7.4 STUDY ENDPOINTS

7.4.1 Primary Endpoint

The primary study endpoint is the change in HRQL at month 24 compared with baseline, as measured by the MSIS-29.

7.4.2 Secondary Endpoints

The secondary variables are clinical outcomes, PROs, and health economics outcomes.

Clinical Outcomes:

Number of relapses (at baseline), at each visit and at month 24

Patient reported outcomes:

• Fatigue: change in Fatigue score, assessed using the MFIS-5, at each visit (except visit 2) and at month 24 (MFIS-5) compared with baseline

- Anxiety/Depression: Change in anxiety/depression at each visit (except visit 2) and at month 24 compared with baseline, as measured by the HADS
- Cognition: Change in cognition at each visit and at month 24 compared with baseline, as measured by the SDMT.
- Sexual Function: Change in intimacy and sexual health at each visit and at month 24 compared with baseline as measured by MSISQ-19
 - Treatment satisfaction: change in TSQM v1.4 score over time, from baseline to each visit (except visit 2) and month 24.
- In patients switching from another DMT: change in TSQM from baseline to month 6 and to month 24
- For naïve patients: change in TSQM from month 6 to month 24
- Disability accumulation: change in PDDS over time at each visit (except visit 2) and at month 24 compared with baseline
- Treatment adherence: number of missed doses of Aubagio®

Health economics outcomes:

- Number of scheduled and unscheduled HCP encounters
- Number of emergency visits
- Change in work capacity reported using the HRPQ-MS at months 12 and 24 compared with baseline.

7.4.3 Safety Measurements and Variables

AEs, SAEs, and AESIs recorded at each visit according to standard clinical practice. Patients will be followed with laboratory monitoring in a regular healthcare setting in line with local approved label requirements and RMP for Aubagio®.

In addition the sites may telephone the patient every 3 months during the study in order to follow up on potential AEs/AESIs/SAEs. The results of these calls will be documented in the study CRF.

7.4.4 Appropriateness of Measurements and Variables

The selected variables and measurements focusing on PROs of HRQoL, disease progression, treatment satisfaction, and clinical effectiveness represent an appropriate approach and setting for this post market authorization observational study in routine medical care collecting real-life outcomes in patients with RRMS who are being treated with Aubagio®. Completing all the questionnaires takes approximately 45 minutes, but as per patient convenience, questionnaires can be completed within one week prior to the date of the scheduled visit; each questionnaire can be completed on a different day.

7.4.4.1 Expanded Disability Status Scale

Patient disability is evaluated using the EDSS, which has long been considered the standard for assessing disability in patients with MS [21]. The EDSS must be performed by a qualified practitioner.

The EDSS is an ordinal clinical rating scale which ranges from 0 (normal neurologic examination) to 10 (death due to MS) in half-point increments. Briefly, the assessing neurologist rates 7 functional systems (pyramidal, cerebellar, brainstem, sensory, bowel and bladder, visual ratings in conjunction with observations and information concerning the patient's mobility, gait, and use of assistive devices to assign an EDSS score.

Version number: Final 2.0

EDSS steps 1.0 to 4.5 refer to people with MS who are fully ambulant, while EDSS steps 5.0 to 9.5 are defined by the impairment to ambulation.

7.4.4.2 Multiple Sclerosis Impact Scale (MSIS-29)

The MSIS-29 is a scale that measures the physical (20 items) and psychological (9 items) impact of MS that was developed and validated by members of the Multiple Sclerosis Society of Great Britain and Northern Ireland [22, 23]. Two summary scores (i.e., the physical scale and the psychological scale) are calculated by summing up individual items in each scale and transforming the scores into a 0-100 scale. High scores indicate a higher impact of MS on the patient's physical and/or psychological health. It takes approximately 5 to 10 minutes to complete.

7.4.4.3 Modified Fatigue Impact Scale – 5 (MFIS-5)

The MFIS-5 consists of a subset of 5 questions from the 21 item MFIS instrument that focus on physical and mental fatigue. Patient answers are scored from 0 (never) to 4 (almost always). Administration time is 2-3 minutes for the abbreviated version [24].

7.4.4.4 Hospital Anxiety and Depression Scale (HADS)

The HADS is a 14-item self-report scale that was designed to screen for mood disorders in general (non-psychiatric) medical outpatients [25, 26]. It focuses on subjective disturbances of mood rather than physical signs and aims at distinguishing between depression and anxiety. The scale consists of depression and anxiety subscales, each with 7 items. Each subscale has a score ranging from 0-21. Items are rated from 0-3, generating a scale range of 0 to 42 points, with higher scores representing greater symptom severity. Subscales scores of 0-7 indicate normal levels of anxiety and depression; 8-10 indicate borderline abnormal anxiety and depression levels and 11-21 suggest abnormal levels of anxiety and depression. It takes approximately 2 to 5 minutes to administer.

7.4.4.5 Symbol Digit Modality Test (SDMT)

The SDMT has been designed to detect cognitive impairment. Brief and easy to administer, the SDMT has demonstrated remarkable sensitivity in detecting not only the presence of brain damage, but also changes in cognitive functioning over time and in response to treatment.

The SDMT involves a simple substitution task that normal children and adults can easily perform. Using a reference key, the examinee has 90 seconds to pair specific numbers with given geometric figures. Responses can be written, oral, and for either response mode, administration time is approximately 5 minutes.

7.4.4.6 Multiple Sclerosis Intimacy and Sexuality Questionnaire (MSISQ-19)

The MSISQ -19 is composed of 19 self-report items measuring the influence of MS symptoms on sexual activity and satisfaction and how they have interfered with the patient's sexual life over the preceding six months. The instrument is divided into three subscales: SD1, for primary sexual dysfunction (items 12, 16, 17, 18, and 19); SD2,

Property of the Sanofi group - strictly confidential

Version number: Final 2.0

secondary (items 1, 2, 3, 4, 5, 6, 8, 10, and 11), and SD3, tertiary (items 7, 9, 13,14, and 15). Each item is rated from 1–5 based on the Likert scale (1 = never; 2 = seldom; 3 = sometimes; 4 = often, and 5 = always); a final score is generated by the summation of the scores across items. The higher the score, the greater the impact of SD on patients' lives.

7.4.4.7 Treatment Satisfaction for Medication Version 1.4 (TSQM v1.4)

The TSQM v1.4 is a global satisfaction scale which is used to assess the overall level of patient satisfaction or dissatisfaction with the medication that the patients are receiving. The TSQM v1.4 includes 14 questions in 4 domains: Effectiveness (Q1 to Q3); Side Effects (Q4 to Q8); Convenience (Q9 to Q11) and Global Satisfaction (Q12 to Q14) [27].

7.4.4.8 Patient Determined Disease Steps (PDDS)

The PDDS is a PRO of disability in MS and was developed by researchers associated with the Patient Registry of the North American Research Committee on MS. This instrument shows a strong correlation with EDSS scores [28]. The PDDS has 9 ordinal levels ranging between 0 (normal) and 8 (bedridden), and PDDS scores can be converted into EDSS scores as well as classifications of mild, moderate, or severe disability.

Administration time will vary depending upon the ability of the patient. Total administration time should be approximately 1 to 5 minutes.

7.4.4.9 Health Related Productivity Questionnaire-MS Version 2 (HRPQ-MS) v2

The HRPQ-MS v2 is a comprehensive instrument that measures several aspects of health-related lost productivity, such as absenteeism and attendance for paid and unpaid work, and long-term loss of workforce participation. It was designed for patients who have a particular disease and/or are being treated for the disease. The HRPQ-MS v2 consists of 9 questions that can be divided into 4 sections:

- Patient's employment status (full-time, part-time, not currently employed)
- Number of hours missed due to the disease/treatment, and percent of impact of the disease/treatment on work output (patients employed full- or part-time)
- Impact of the disease/treatment on productivity related to household chores (patients not currently employed)
- Disease history, including whether the disease/treatment forced the patient to change working situation (e.g., go from full-time to part-time, quit working, etc.).

The HRPQ-MS v2 asks patients to report lost productivity in the past week to minimize recall bias. Administration time is approximately 5 minutes at baseline collection and 3 to 4 minutes at follow-up.

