6.2 SECONDARY

To describe the change in the following PROs at 2 years, in patients commencing on treatment with Aubagio® in routine clinical practice for RRMS:

- Fatique
- Anxiety and depression
- Cognition
- Sexual dysfunction
- Disease progression
- Treatment satisfaction
- Treatment adherence

To describe the number of relapses during the two year study period in patients commencing on treatment with Aubagio® in routine clinical practice for RRMS

To describe health economic outcomes in patients with RRMS treated with Aubagio® assessed by the number of scheduled and unscheduled healthcare provider (HCP) encounters and emergency visits as well as productivity loss.

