14.3.1.2 Secondary Analysis

The changes from baseline to month 24, and to each follow-up visit before 24 months visit, in TSQM v1.4, PDDS, MFIS-5, HRPQ-MS v2, MSISQ-19, SDMT and HADS will be tested using the t-distribution. The mean changes between study visits with the corresponding 95% confidence interval will be given. If required, an ANCOVA, adjusting for baseline covariates will be performed. A p-value below 0.05 will be considered statistically significant. The evolution of PRO scores during the follow-up period will be also represented graphically.

In addition to PRO scores, the same statistical methods will be used to analyse number of missed doses of Aubagio® (adherence), number of relapses, number of HCP encounters and number of emergency room visits.

Additional exploratory pre-specified analysis of the secondary endpoints will be performed in at least 4 specific subgroups: treatment naïve patients, patients previously treated with a MS DMT within the past 2 years, injectable switch patients and oral switch patients.

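### The t-test fixed for change in HRPQ-MS does not fit an instrument that branches by employment: a paid-work mean change covers only patients employed at both visits

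*Protocol*

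**What the plan says.** Section 6.2 sets an objective that includes "emergency visits as well as productivity loss". Section 7.4.2 turns this into a secondary endpoint: "Change in work capacity reported using the HRPQ-MS at months 12 and 24 compared with baseline".

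Section 14.3.1.2, repeated in the synopsis, fixes the method. Changes "in TSQM v1.4, PDDS, MFIS-5, HRPQ-MS v2, MSISQ-19, SDMT and HADS will be tested using the t-distribution", mean changes are given with 95% confidence intervals, and "A p-value below 0.05 will be considered statistically significant". No HRPQ-MS item, score or denominator is named.

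Section 7.4.4.9 describes nine questions in four sections:

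- "Patient's employment status (full-time, part-time, not currently employed", a categorical item;
- "Number of hours missed due to the disease/treatment, and percent of impact of the disease/treatment on work output (patients employed full- or part-time", numeric and for the employed only;
- "Impact of the disease/treatment on productivity related to household chores (patients not currently employed", for those without a job only;
- a history section that records whether disease or treatment forced a change in working situation, also categorical.

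No total score is described. The same section says the instrument covers long-term loss of workforce participation. Section 14.3.1 gives the general rule that categorical data are summarised by frequency and percent.

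**The concern.** A t-test on change needs the same numeric quantity from the same patient at two visits. On this instrument the numeric quantities depend on employment status at each visit, and employment status is itself part of the outcome. A patient employed at baseline and out of work at month 24 answers the paid-work items once and the household items once, so neither gives a difference. If that patient stopped work because of MS, the largest productivity loss is the one missing from the tested mean.

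A forced move from full-time to part-time is a milder case. The patient keeps a pair, but the hours given up need not be reported as missed, because they are no longer due.

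The mean in continuing workers could then show no loss, or even a gain, while patients leave work. The study has no control group (Section 7.1) against which such a pattern would stand out.

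**Working it through.** **The plan's own figure.** The protocol gives no figure for HRPQ-MS. Its only computed figure is the MSIS-29 precision in Section 14.1: 1.96 × 20 / √100 = 3.92, stated as about 4. It reproduces and has no bearing here.

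**Which patients have a pair** (from Section 7.4.4.9):

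| Baseline → follow-up | Paid-work items | Household items |
|---|---|---|
| Employed → employed | pair | none |
| Employed → not employed | baseline only | follow-up only |
| Not employed → employed | follow-up only | baseline only |
| Not employed → not employed | none | pair |

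Both groups that change state drop out of any paired mean. The two categorical sections have no mean change at all.

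**Size, as illustration only.** The documents give no job-loss rate, weekly hours or share employed, so every input below is assumed. Among patients employed at baseline, let L be the share who leave work because of MS, H the weekly hours, h0 the hours already missed at baseline, and d the mean change in hours missed among those still employed. Count a lost job as H hours lost.

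- Mean change over all baseline workers = (1 − L) × d + L × (H − h0)
- Paired mean = d
- Understatement = L × (H − h0 − d)

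Take H = 35 and h0 = 4. Positive values mean more hours lost.

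| L | Understatement, d = 0 | Mean over all baseline workers, d = −1 |
|---|---|---|
| 5% | 0.05 × 31 = 1.55 | −0.95 + 1.55 = +0.6 |
| 10% | 0.10 × 31 = 3.1 | −0.90 + 3.1 = +2.2 |
| 20% | 0.20 × 31 = 6.2 | −0.80 + 6.2 = +5.4 |

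In the last column the paired mean reports an improvement of 1 hour, while the whole baseline-employed group has lost hours.

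**Dependence on cause.** If 10% leave work but only half of them because of MS, L is 5% and the understatement at d = 0 is 1.55. If none leave because of MS, it is 0.

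**Number of pairs.** Section 8.1 plans up to 100 patients. If 50% to 70% are employed at baseline (assumed) and 10% of these leave work, pairs fall from 50–70 to 45–63, before other missing data.

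**The case against.** The strongest reply is that Section 14.3.1.2 names the instrument and not an item. Choosing the variable, scoring a branched questionnaire and setting denominators is ordinary SAP work; the synopsis defers further detail to the SAP, and Section 14.3 describes itself as the specification for it. This stands in part. A reader might infer that the protocol plans a t-test on the employed-only items, but it does not say so. What it does fix is mean change with a t-test, and Section 7.4.4.9 describes no quantity defined for all patients to which that could apply. The paid-work items are the natural reading of work capacity, and they carry the selection.

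The second reply is that job loss stays in the data. Employment status and disease-forced change are collected and would be tabulated under Section 14.3.1. This stands. It confines the problem to the tested mean. Frequencies by visit are nevertheless not transitions: patients who start work can offset patients who stop, and the cause is not linked to the change.

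The third reply is that a mean among continuing workers is a legitimate summary. That is so if it is labelled as conditional. The protocol gives no such label.

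Finally, this is one of many secondary outcomes in a descriptive study, and the sample size does not rest on it. That is fair and limits the weight of the point.

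**Conclusion.** The point holds in a limited form. The protocol fixes a mean-change t-test for an instrument whose numeric items are split by employment. Applied to the paid-work items, the test is conditional on being employed at both visits and cannot show the workforce loss that the instrument is said to measure. If patients leave work because of MS, the mean understates lost productivity.

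Two stronger readings are not supported. One is that lost productivity is understated throughout the report; Section 14.3.1 would still show employment status. The other is that the understatement can be put at a definite number of hours. The 1.55 to 6.2 hours per week above rests wholly on assumed inputs, is zero if no exit is MS-related, and takes no account of patients who start work.

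The change is worth making because the selection is foreseeable and a better analysis can be built from items that Section 7.4.4.9 already lists.

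**What to change.** In Section 14.3.1.2 and the synopsis:

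1. Take HRPQ-MS v2 out of the general t-test list.
2. Make the main analysis of change in work capacity a transition table from baseline to month 12 and to month 24 (full-time, part-time, not employed) for all patients with data at both visits.
3. From it, report the proportion of patients employed at baseline who reduced or left work because of disease or treatment, with a 95% confidence interval.
4. Report paired change in hours missed and percent impact on output as supplementary, labelled as conditional on employment at both visits, with the number of pairs.
5. Analyse the household items separately.

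Do not impute usual baseline hours for patients who leave unless usual hours are shown to be collected. Section 7.4.4.9 does not list them, and charging a full week to someone who moved to part-time would overcount the loss.

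The cost is a few lines of text and one more table, and the paid-work mean loses its status as the tested result. The proportion in item 3 will be imprecise: at 10% among an assumed 50 to 70 baseline workers, the approximate half-width is 1.96 × √(0.10 × 0.90 / 50) = 8.3 percentage points, or 7.0 with 70. One check is needed first. Section 7.4.4.9 gives a shorter completion time at follow-up than at baseline, so confirm that the forced-change item is asked at months 12 and 24. The transition table itself needs only employment status at each visit.

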8 SELECTION OF PATIENTS

8.1 SAMPLE SIZE

It is planned to recruit up to 100 eligible patients at approximately 20 sites in the UK. See sample size calculation provided in section 14.1.

8.2 INCLUSION CRITERIA

- I 01. Adult patients (≥18 years old) with RRMS according to a neurologist's diagnosis, where the physician together with the patient have decided to start treatment with Aubagio® according to the approved SmPC.
- I 02. Initiated Aubagio® treatment for the first time within 4 weeks of study entry
- 103. Patients who have signed written informed consent
- 104. Patients who are willing and able to complete the questionnaires for the full duration of the study

Note: (if a designated caregiver is available to assist the patient, they may physically complete the questionnaire for the patient)

8.3 EXCLUSION CRITERIA

- E 01. Patients with contraindications to Aubagio® treatment according to the SmPC
- E 02. Patients who are currently participating in an investigational interventional study if, in the judgment of investigator, such participation would interfere with the current study
- E 03. Patients who are unwilling or unable to complete any questionnaire to be used in the study
- E 04. Women of child bearing age who are not willing to use and effective form of contraception

8.4 MODALITIES OF RECRUITMENT

Investigators at participating sites will identify patients with relapsing remitting forms of MS who are eligible for Aubagio® treatment according to the approved SmPC. Upon the decision to start treatment with Aubagio®, there will be consecutive recruitment of all eligible patients who are willing to participate. Recruitment of patients into the study must never be an incentive to start treatment with Aubagio®. Investigators will be asked to track the sequence of events, making sure the decision to start treatment with Aubagio® occurs before patients are informed about potential study participation. The study visit schedule will be performed according to the site specific clinical practice.

8.5 WITHDRAWALS AND DROPOUTS

Patients may withdraw from treatment with Aubagio ® if they decide to do so, at any time and irrespective of the reason, or this may be the Investigator's decision. All efforts should be made to document the reasons for treatment discontinuation, and this should be documented in the eCRF.

If a patient discontinues Aubagio® treatment before month 24, the V6 (month 24/EOS visit) evaluations should be performed as soon as possible.

Patients who have withdrawn from the study cannot be re-included (treated) in the study. Their inclusion numbers must not be reused.

Version number: Final 2.0

Patients who prematurely discontinue participation in the study will not be replaced. The Investigator may continue to enrol patients in the study for the duration of the recruitment phase.

The Statistical Analysis Plan (SAP) will specify how patients who are lost to follow-up for their primary endpoints will be considered.

9 SELECTION OF INVESTIGATORS

Investigators who are experienced in the treatment of patients with RRMS will undergo a feasibility assessment performed by Sponsor representatives. Study sites will be selected in facilities where qualified physicians diagnose, treat, and manage healthcare for patients with MS, including treatment with Aubagio® and other DMT as their routine practice. Upon qualification and confirmation to comply with the protocol-defined requirements, Investigators will be selected and the contract will be signed. Thereafter operational activities to start and conduct this study will be performed.

10 TREATMENTS

The prescription of therapies is under the responsibility of the Investigator only; the Sponsor will not provide Aubagio® for this study. Administration of Aubagio® and monitoring of patients according to the label will be the sole responsibility of the treating Investigator.

The patients who will be enrolled in the study will be selected among the patients for whom the Investigator has decided to prescribe Aubagio® prior to, and independently from, study entry.

The Investigator should refer to the SmPC for any information on treatment prescribed.

This agreement also implies that all labelled restrictions such as contraindications, special warnings and precautions for use, interaction with other medicinal products, and other forms of interactions and instructions for pregnancy and lactation will be followed. Concomitant therapy may be administered according to the approved SmPC and at the discretion of the Investigator. Any other concomitant MS DMTs are prohibited, except that symptomatic MS therapies or corticosteroids for treatment of relapse are allowed.

11 DATA COLLECTION

Data to be collected, and the corresponding schedule of recordings, are presented in Section 2.2.

11.1 DATA COLLECTION SCHEDULE

Data collection should occur as close to the visit schedule outlined in Section 2.2 as possible, with all data collected as outlined for the applicable visit. In the case of premature termination of study participation, data collection for month 24 (V6/EOS visit) should occur as soon as possible.

